### **4.3. Inclusion Criteria: Psoriasis Multiple Dose Cohorts**

Subject eligibility should be reviewed and documented by an appropriate member of the investigator's study team before subjects are included in the study.

Subjects must meet all of the following inclusion criteria to be eligible for enrollment into the study:

1. Female subjects of non-childbearing potential and/or male subjects with a diagnosis of plaque psoriasis who are between the ages of 18 and 65 years, inclusive.
2. Female subjects of non-childbearing potential must meet at least 1 of the following criteria:
  - a. Achieved postmenopausal status, defined as follows: cessation of regular menses for at least 12 consecutive months with no alternative pathological or physiological cause; and have a serum FSH level confirming the post menopausal state.
  - b. Have undergone a documented hysterectomy and/or bilateral oophorectomy.
  - c. Have medically confirmed ovarian failure.

All other female subjects (including females with tubal ligations) are considered to be of childbearing potential.

3. Body Mass Index (BMI) of 17.5 to 37.5 kg/m^2; and a total body weight >50 kg (110 lbs).
4. Evidence of a personally signed and dated informed consent document indicating that the subject has been informed of all pertinent aspects of the study.
5. Subjects who are willing and able to comply with scheduled visits, treatment plan, laboratory tests, and other study procedures.
6. Have a diagnosis of plaque psoriasis for at least 6 months prior to first study dose.
7. Have plaque-type psoriasis covering at least 15% of total BSA at Day -1 (prior to randomization in the study).
8. Have a PASI score of 12 or greater at Day -1 (prior to randomization in the study).
9. Be a candidate for phototherapy or systemic treatment of psoriasis (either naïve or history of previous treatment) in the opinion of the investigator.
10. Must agree to avoid prolonged exposure to the sun and avoid other ultraviolet light sources during the study (eg, tanning beds).

11. No evidence of active or latent or inadequately treated infection with Mycobacterium tuberculosis (TB) as defined by the following:
  - a. negative Interferon Gamma Release Assay (IGRA) (with the following acceptable assays: QuantiFERONR-TB Gold (QFT-G) test, T-SPOT TB, QuantiFERON-TB Gold In-Tube test (QFT-GIT)) performed during Screening or within 3 months prior to Day 1.

AND

- b. No history of either untreated or inadequately treated latent or active TB infection.

If a subject has previously received an adequate course of therapy for either latent (9 months of isoniazid in a locale where rates of primary multi-drug resistant TB infection are <5%) or active TB infection, a QFT Gold test need to be obtained, but a chest radiograph or other appropriate image negative for active TB infection, must still be obtained if not done so within the prior 3 months.

A subject who is currently being treated for either latent or active TB infection is to be excluded.

#### **4.4. Exclusion Criteria: Psoriasis Multiple Dose Cohort**

Subjects presenting with any of the following characteristics/conditions will not be included in the study:

1. Currently have non-plaque forms of psoriasis, eg, erythrodermic, guttate, or pustular psoriasis.
2. Have current drug-induced psoriasis, eg, a new onset of psoriasis or an exacerbation of psoriasis from beta blockers, calcium channel blockers, antimalarial drugs or lithium.
3. If planned initiation of, or changes to, concomitant medication that could affect psoriasis (eg, beta blockers, calcium channel blockers, antimalarial drugs or lithium) are to occur within 2 weeks prior to randomization and/or during the study.
4. Subjects with ANY of the following abnormalities in clinical laboratory tests at screening, as assessed by the study-specific laboratory and confirmed by a single repeat, if deemed necessary:
  - a. Hemoglobin:
    - If the hemoglobin level is greater than 5% below the lower limit of normal (LLN), subject is to be excluded;

- If the hemoglobin level is within 5% below the LLN, iron and folate levels are to be measured: if iron and/or folate levels are below the LLN, subject is to be excluded.
  - b. Absolute neutrophil count of  $<2 \times 10^9/L$  ( $<2000/mm^3$ ).
  - c. Platelet count below the LLN.
  - d. Serum creatinine level above the upper limit of normal or an estimated Glomerular Filtration Rate (GFR) value  $\leq 80$  mL/min, based on the Cockcroft-Gault calculation, at Screening (see [Appendix 2](#)).
  - e. Aspartate aminotransferase (AST)/serum glutamic oxaloacetic transaminase (SGOT) or alanine aminotransferase (ALT)/serum glutamic pyruvic transaminase (SGPT)  $\geq$  values more than 1.5 times the upper limit of normal.
  - f. Fasting glucose  $>140$  mg/dL.
  - g. Total bilirubin  $\geq 1.5 \times$  ULN; subjects with a history of Gilbert's syndrome may have a direct bilirubin measured and would be eligible for this study provided the direct bilirubin is  $\leq$ ULN.
5. Any psychiatric condition including recent or active suicidal ideation or behavior that meets any of the following criteria:
- Suicidal ideation associated with actual intent and a method or plan in the past year: “Yes” answers on items 4 or 5 of the Columbia suicide severity rating scale (C-SSRS) ([Appendix 9](#)).
  - Previous history of suicidal behaviors in the past 5 years: “Yes” answer (for events that occurred in the past 5 years) to any of the suicidal behavior items of the C-SSRS.
  - Any lifetime history of serious or recurrent suicidal behavior.
  - Suicidal behaviors questionnaire –revised (SBQ-R) ([Appendix 10](#)) total score  $\geq 8$ .
  - Clinically significant depression: patient health questionnaire – 8 items (PHQ-8) ([Appendix 11](#)) when the total score  $\geq 15$ .
  - The presence of any current major psychiatric disorder that is not explicitly permitted in the inclusion/exclusion criteria.
  - In the opinion of the investigator or Pfizer (or designee) exclusion is required.

6. Have current or recent history of severe, progressive, or uncontrolled renal, hepatic, hematological, gastrointestinal, metabolic, endocrine, pulmonary, cardiac, neurological or allergic disease (including drug allergies, but excluding untreated, asymptomatic, seasonal allergies at time of dosing).
7. Will have vaccination with live virus, attenuated live virus, or any live viral components within the 6 weeks prior to the first dose of study drug or is to receive these vaccines at any time during treatment or within 8 weeks following completion of study treatment.
8. Will have routine household contact with individuals who have received vaccination with live virus, or attenuated live virus, for 8 weeks following completion of study treatment.
9. Have a history of any lymphoproliferative disorder (such as Epstein Barr Virus [EBV]-related lymphoproliferative disorder, as reported in some subjects on other immunosuppressive drugs), history of lymphoma, leukemia, myeloproliferative disorders, multiple myeloma, or signs and symptoms suggestive of current lymphatic disease.
10. Have a clinically significant infection currently or within 6 months of first dose of study drug (eg, those requiring hospitalization or parenteral antimicrobial therapy or opportunistic infections), or a history of chronic or recurrent infectious disease.
11. Have or have had symptomatic herpes zoster or herpes simplex within 12 weeks, more than one episode of local herpes zoster, or a history (single episode) of disseminated zoster.
12. Any prior treatment with lymphocyte depleting agents/therapies (such as CamPath® [alemtuzab], alkylating agents [eg, cyclophosphamide or chlorambucil], total lymphoid irradiation, etc).
13. Have any condition possibly affecting oral drug absorption, gastrectomy, or clinically significant diabetic gastroenteropathy.
14. History of regular alcohol consumption exceeding 7 drinks/week for females or 14 drinks/week for males (1 drink = 5 ounces (150 mL) of wine or 12 ounces (360 mL) of beer or 1.5 ounces (45 mL) of hard liquor) within 6 months of Screening.
15. 12-lead ECG demonstrating QTc >450, or a QRS interval >120 msec msec at Screening. If QTc exceeds 450 msec or QRS exceeds 120 msec, the ECG should be repeated two more times and the average of the three QTc (or QRS) values should be used to determine the subject's eligibility.

16. Screening supine blood pressure  $\geq 160$  mm Hg (systolic) or  $\geq 100$  mm Hg (diastolic), following at least 5 minutes of supine rest. If blood pressure (BP) is  $\geq 160$  mm Hg (systolic) or  $\geq 100$  mm Hg (diastolic), the BP should be repeated two more times and the average of the three BP values should be used to determine the subject's eligibility.
17. Herbal supplements and hormone replacement therapy must be discontinued 28 days prior to the first dose of study medication. As an exception, acetaminophen/paracetamol may be used at doses of  $\leq 1$  g/day. Limited use of non-prescription medications that are not believed to affect subject safety or the overall results of the study may be permitted on a case-by-case basis following approval by the sponsor.
18. Donated blood in excess of 500 mL (excluding plasma donations) within 2 months prior to the first dose of study drug.
19. Acute disease state (eg, nausea, vomiting, fever, or diarrhea) within 7 days of Day 1.
20. Have a first-degree relative with a hereditary immunodeficiency.
21. Have any malignancies or have a history of malignancies with the exception of adequately treated or excised non-metastatic basal cell or squamous cell cancer of the skin.
22. Have undergone significant trauma or major surgery within 4 weeks of Screening.
23. Are known to be infected with human immunodeficiency virus (HIV) or hepatitis B or C viruses.
24. Have participated in any other studies with JAK inhibitors within 3 months prior to dosing.
25. In the opinion of the investigator or Pfizer, will be uncooperative or unable to comply with study procedures.
26. Have participated in other studies involving investigational drug(s) within 30 days or 5 half-lives (whichever is longer) prior to study entry and/or during study participation.
27. Other acute or chronic medical or psychiatric condition including recent (within the past year) or active suicidal ideation or behavior or laboratory abnormality that may increase the risk associated with study participation or investigational product administration or may interfere with the interpretation of study results and, in the judgment of the investigator, would make the subject inappropriate for entry into this study.

28. Have any other condition which would make the subject unsuitable for inclusion in the study.
29. Subjects who are investigator site staff members directly involved in the conduct of the study and their family members, site staff members otherwise supervised by the investigator, or subjects who are Pfizer employees, including their family members, directly involved in the conduct of the study.
30. Pregnant female subjects; breastfeeding female subjects; female subjects of childbearing potential.
31. Fertile males subjects who are unwilling or unable to use a highly effective method of contraception as outlined in this protocol for the duration of the study and for at least 28 days after the last dose of investigational product.
32. Use of tobacco/nicotine containing products in excess of  $\geq 5$  cigarettes/day.
33. A positive urine drug screen.
34. Consumption of grapefruit or grapefruit juice or citrus fruits eg, Seville oranges, pomelos within 7 days prior to the first dose of study medication until collection of the final pharmacokinetic blood sample.
35. Require treatment with prohibited concomitant medication(s) listed in [Appendix 3](#) or have received a prohibited concomitant medication in the 4 weeks prior to the first dose of study drug. Subjects receiving non-prohibited concomitant medications for any reason must be on a stable regimen, which is defined as not starting a new drug or changing dosage within 2 weeks or 5 half-lives (whichever is longer) prior to first dose of study drug.
36. Have previously been treated with efalizumab (Raptiva®).
37. Have previously been treated with secukinumab (Cosentyx) or ixekizumab (Taltz).
38. Have previously been treated with ustekinumab (Stelara®).
39. Have received any of the following treatment regimens specified in the timeframes outlined below:

Biologic therapies for psoriasis (including brodalumab) have discontinuation periods determined from approximately 5x half-life of the respective biologic.

**Within 12 weeks of first dose of study drug:**

- Any experimental therapy for psoriasis, psoriatic arthritis, or rheumatoid arthritis.

Exception: Investigational biologics should be discussed with the Pfizer Medical Monitor (or designee) to confirm period of discontinuation required.

- Apremilast (Otezla).

**Within 10 weeks of first dose of study drug:**

- Adalimumab (Humira®);
- Certolizumab pegol (Cimzia®);
- Infliximab (Remicade®);
- Alefacept (Amevive®).

**Within 4 weeks of first dose of study drug:**

- etanercept (Enbrel®).
- Systemic treatments other than biologics that could affect psoriasis (eg, oral or injectable corticosteroids, retinoids, methotrexate, cyclosporine, fumaric acid derivatives, sulfasalazine, hydroxycarbamide (hydroxyurea), azathioprine).
- Phototherapy and psoralens (PUVA).
- Other – intramuscular gold, herbal medications.

**Within 2 weeks of first dose of study drug:**

- Topical treatments that could affect psoriasis (eg, corticosteroids, tars, keratolytics, anthralin, vitamin D analogs, and retinoids). Treatments allowed are: non-medicated emollients for use over the whole body, low or least potent(Class 6 or 7) topical corticosteroids for the palms, soles, face, and intertriginous areas only; tar and salicylic acid preparations for the scalp only, or shampoos free of corticosteroids for the scalp only. More potent topical steroids (Class 5-2) could be considered on an as-needed basis on the face, scalp, and genital areas only after discussion with the Sponsor's Medical Monitor.
- Phototherapy with UVB (narrowband or broadband).

#### **4.5. Randomization Criteria**

Subjects will be randomized into the study provided they have satisfied all subject eligibility criteria.

Healthy subjects will be randomized (once) into the SAD period, at which time, they will receive treatment assignment (active PF-06826647 dose level or placebo) for both the SAD and MAD periods. Subjects will receive the same blinded treatment assignment (ie, the same

dose level of active PF-06826647 or placebo) throughout in both the SAD (Period 1) and MAD (Period 2) periods. Optional BID cohort subjects may be directly randomized to the twice daily 10 day treatment regimen once confirmation of eligibility criteria occurs, without the need to participate in a single dose period.

- The randomization ratio for the cohorts in the healthy subject SAD/MAD segment will be 3: 1 (PF-06826647:Placebo).
- The randomization ratio for the planned psoriasis multiple dose cohorts will be 2:1 (PF-06826647:Placebo).

#### **4.6. Lifestyle Requirements**

The following guidelines are provided:

##### **4.6.1. Meals and Dietary Requirements**

- Administration of investigation product will be in fasted state in SAD period and under standard meal condition in MAD (QD and BID) period and in Psoriasis cohorts. Based on the emerging PK, CCI [REDACTED] and safety data, the meal condition requirement in SAD, MAD and Psoriasis cohorts may be adjusted.
- Under any meal condition, subjects will not be allowed to eat or drink grapefruit or grapefruit-related citrus fruits (eg, Seville oranges, pomelos) from 7 days prior to the first dose of study medication until collection of the final pharmacokinetic blood sample.
- Except when the investigational product is dosed under high fat meal condition, the total daily nutritional composition should be approximately 55% carbohydrate, 30% fat and 15% protein and the daily caloric intake per subject should not exceed approximately 3200 kcal while confined.

##### **Dosing under fasted condition:**

- Subjects must abstain from all food and drink (except water) at least 8 hours prior to any safety laboratory evaluations (as indicated in the study [Schedule of Activities](#)) and 8 hours prior to the collection of the pre-dose pharmacokinetic sample. Water is permitted until 1 hour prior to investigational product administration.
- The investigational product should be administered with approximately 240 mL (8 fluid ounces) of ambient temperature water. Additional water may be allowed if needed to administer the entire dose.
- Water may be consumed without restriction beginning 1 hour after dosing. Non-caffeinated drinks (except grapefruit or grapefruit-related citrus fruit juices – see above) may be consumed with meals and the evening snack.
- Lunch will be provided approximately 4 hours after dosing.

- Dinner will be provided approximately 9 to 10 hours after dosing.
- An evening snack may be permitted.

**Dosing under standard meal condition:**

Following an overnight fast of at least 8 hours, subjects should start breakfast approximately 25 minutes prior to the morning administration of the investigational product when dosing in the fed condition. In BID cohort, subjects should start dinner approximately 25 minutes prior to the evening administration of the investigational product, when dosing in the fed condition. The breakfast and dinner (BID period only) will be consumed over approximately 20 minutes with study drug administered within approximately 5 minutes after completion of the meal. Subjects will be encouraged to eat the full standard meal on PK profile assessment days (Days 1 and 10) and are required to eat a minimum of approximately 80% of the meal preceding dosing. Subjects will be encouraged to eat the full standard meal and are required to eat a minimum of approximately 50% of the meal on all other dosing days. Subjects should be encouraged to eat any snack that will precede dosing. The study treatment should be administered with approximately 240 mL (8 fluid ounces) of ambient temperature water. Additional water may be allowed if required to administer the entire dose. No food will be allowed for at least 2 hours post-dose.

- Water can be allowed as desired except for 1 hour after investigational product administration. There are no water restrictions prior to dosing for subjects dosed under fed conditions.
- Lunch will be provided approximately 4 hours after dosing.
- Dinner will be provided approximately 9 to 10 hours after dosing.
- An evening snack may be permitted.

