Body weight	X																	X																	X			
Height	X																																					
CCI																																						
Blood Safety Labs (chemistry and hematology) (fasting) h	X	X			X		X			X		X				X	X	X					X					X	X		X							
CCI																																						
CCI																																						
Lipid Panel (fasting) i	X	X								X						X	X	X																		X		
Urinalysis	X	X		X			X					X				X	X	X		X	X	X	X													X		
Urine Drug Test	X	X																																				
ECG j	X	X	X					X		X					X	X	X	X	X	X	X	X	X	X	X	X	X	X							X			
Vital signs: Supine single PR, BP and Oral Temperature k	X	X	X	X	X	X	X	X	X	X	X	X	X	X	X	X	X	X	X	X	X	X	X	X	X	X	X	X	X	X	X	X	X	X	X	X		
Study Treatment Administration l			X	X	X	X	X	X	X	X	X	X	X	X	X	X	X	X																				
PK Blood Sampling m			X					X								X	X	X	X	X	X	X	X	X	X	X	X	X										
CCI																																						
CCI																																						
CCI																																						

- C** [REDACTED]
- C** [REDACTED]
- f. Target lesion and regional photography.
  - g. A full physical examination may be done at screening or may be deferred to Day -1 (prior to randomization) at the discretion of the investigator. A full physical exam should also be performed at Day 28. A limited physical exam can be performed at all other times if no findings during previous examination or new/open AE, at the discretion of the investigator.
  - h. Safety labs (chemistry and hematology) are collected following at least 8 hours of fasting (on Day 28, fasting requirement applies to hour 0 only).
  - i. Lipid panel (Cholesterol, Triglycerides, HDL, and LDLc): Fasting requirement of at least 8 hours.
  - j. Triplicate ECGs will be collected on Day 1, Day 28, and Day 29. Single ECGs will be collected at all other time points/visits.
  - k. Vitals taken on Days 1-28 will be performed at approximately 2 hours post-dose; vitals will also be taken on Day 29, 35, 42 and 56/ET (follow-up) visits.
  - l. Study treatment administration occurs once daily for 28 days, starting on Day 1 and ending on Day 28.
  - m. Blood samples collected for PK predose on Days 1, 7, 14, 21, and 28 (time 0), and on the morning of Day 29 and Day 35.

- C** [REDACTED]
- o. Subjects who have recent or active suicidal ideation or behavior will be excluded from the study (refer to [Section 4.4](#)).

**C** [REDACTED]

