Administration of blinded study medication occurs on study Days 1 through 28. On study Days 1 through 21, all assessments listed in the [schedule of activities](#) occur pre-dose. On study Days 1 through 21, at 2 hours post dose, obtain vital signs including supine blood pressure, pulse rate (after at least 5 minutes of rest), and oral temperature. Assess symptoms by spontaneous reporting of adverse events and by asking the subjects to respond to a non-leading question such as “How do you feel?”. On study Day 28, the assessment time course depicted in the [schedule of activities](#) should be followed. Assessments on Day 28, hour 0, occur pre-dose.

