Preliminary pharmacokinetic data on Day 1 and Day 10 following multiple oral administration of PF-06826647 with standard meal at 30, 100 and 400 mg once daily (QD) are summarized in Table 2. By contrast with the PK parameters reported in Table 1, single dose administration with standard meal modestly increased the exposure of PF-06826647 by approximately 1.6 and 1.5 fold for AUC and Cmax, respectively at 400 mg. The increase in exposure at steady state appears to be less than proportional with increase in dose. Multiple dosing over 10 days achieved steady state with modest accumulation (1.3 and 1.2 fold for AUC and Cmax at 400 mg, respectively).

**Table 2. Preliminary Summary of Draft Plasma PK Parameters of PF-06826647 Following Multiple Oral QD Dose Administration of PF-06826647 for 10 Days in Healthy Subjects (Fed-Standard Meal)**

Dose (mg)	Day 1		Day 10		
	C max (ng/mL)	AUC 24 (ng.hr/mL)	C max (ng/mL)	AUC 24 (ng.hr/mL)	t 1/2 hr
30	84 (24)	664 (25)	85 (27)	752 (32)	9 (67)
100	267 (20)	1811 (23)	263 (30)	1950 (34)	7 (38)
400*	520 (30)	3488 (58)	689 (14)	4919 (32)	4(13)

Geometric mean (%CV) for all except arithmetic mean (%CV) for t1/2; Abbreviations: %CV = percent coefficient of variation; NR = Not Reportable. AUC24= Area under the concentration-time curve from time zero to 24 hours post single dose; Cmax = Peak plasma concentration; \*Partial data (only 4 subjects up to Day 11).

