In addition, based on data observed to date in healthy subjects (see [Section 1.3.2](#)) these doses are expected to be safe and well tolerated. Although, based on in vitro data, the average inhibition of EPO (total IC50 = 547 nM) is expected to be approximately 35% and 58% at 100 and 400 mg respectively, no clinically significant changes in hemoglobin were observed in healthy subjects at the same dose. Based on the observed steady state free exposures (Cmax,ss and AUC24,ss), 400 mg QD is expected to provide margins of about 7-fold for Cmax,ss and about 9-fold for AUC24,ss relative to the free exposure in rat on Day 29 (NOAEL).

The initial psoriasis cohort will commence at 400 mg QD PF-06826647 for 28 days. Dosing of the second psoriasis cohort will occur after completion of 400 mg psoriasis Cohort 28 day dosing, while the follow up periods of the two cohorts may be parallel or staggered based on operational considerations. Following interim analysis review of efficacy data from 21 subjects (14 active and 7 placebo) completing through study Day 28 in the 400 mg psoriasis cohort, the PF-06826647 dose level for the next psoriasis cohort may be adjusted within the range of safe and well tolerated doses established in healthy subjects.

The tablets administered in psoriasis subjects will be the same as the tablet administered to healthy subjects. The subjects will be required to take the tablets in the morning with standard meal in order to achieve higher exposure.

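### The meal minimum for PK profile days names only the MAD days (1 and 10), so, read literally, the psoriasis Day 28 profile falls under the looser minimum

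*Protocol*

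**What the plan says.** Protocol Section 4.6.1 places dosing "under standard meal condition in MAD (QD and BID) period and in Psoriasis cohorts", so its standard-meal paragraph is the working rule for psoriasis subjects. That paragraph sets two levels. It urges that subjects "eat the full standard meal on PK profile assessment days (Days 1 and 10) and are required to eat a minimum of approximately 80" per cent of the meal preceding dosing. For the rest of the dosing period they are again encouraged to finish the meal, but are only "required to eat a minimum of approximately 50% of the meal on all other dosing days". Section 5.5 refers back to 4.6.1 and gives no fraction of its own.

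The psoriasis Schedule of Activities states that "Study treatment administration occurs once daily for 28 days, starting on Day 1 and ending on Day 28". Footnote m lists pre-dose PK samples on Days 1, 7, 14, 21 and 28, then Day 29 and Day 35. Day 28 follows a timed course: "Assessments on Day 28, hour 0, occur pre-dose", and the columns then run from 0.5 to 24 hours.

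Psoriasis plasma PK is a secondary objective (Protocol Section 2; SAP Section 6.2.2). The psoriasis dose rationale in Section 1.3.4.1 explains the fed dosing: "The subjects will be required to take the tablets in the morning with standard meal in order to achieve higher exposure". Section 1.3.2 reports that "single dose administration with standard meal modestly increased the exposure of PF-06826647", by about 1.6-fold for AUC and 1.5-fold for Cmax at 400 mg, the dose of the first psoriasis cohort.

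**The concern.** The bracketed days are a closed list, and the next sentence assigns every remaining dosing day to the lower minimum. The list fits the MAD schedule but not the psoriasis schedule. A site applying it literally to a psoriasis subject would enforce the higher minimum on two days without a profile and accept half a breakfast on the one day that has a profile.

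Two uses of the data are exposed. First, PK is summarised by study population, healthy and psoriasis (Protocol Section 9.3.1; SAP Section 6.4), and the two profiles would be taken under different required minimums. Second, Section 3.1.2 calls for review of PK up to Day 28 in the 400 mg psoriasis cohort before any Cohort 2 dose adjustment. If intake is lower or more variable on Day 28, exposure may look lower or more scattered for a reason unrelated to psoriasis.

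**Working it through.** **1. Is Day 28 the psoriasis profile day?** Table 10 gives 14 treatment-period PK samples and 1 follow-up sample at 4 mL, 60 mL in all. Count from the schedule: pre-dose on Days 1, 7, 14 and 21 = 4; Day 28 series at 0, 0.5, 1, 2, 4, 6, 8, 12, 16 and 24 h = 10 (the 24 h sample is Day 29); Day 35 = 1. Then 4 + 10 = 14, 14 + 1 = 15, and 15 × 4 mL = 60 mL. The plan's figure is reproduced, with the full series on Day 28 and no PK sample on Day 10.

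**2. Meal rule against sampling**

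| Cohort and day | PK sampling | Required minimum, read literally |
|---|---|---|
| MAD Days 1 and 10 | serial profile | about 80% |
| Psoriasis Day 1 | pre-dose only | about 80% |
| Psoriasis Day 10 | none | about 80% |
| Psoriasis Days 7, 14, 21 | pre-dose only | about 50% |
| Psoriasis Day 28 | serial profile, 0 to 24 h | about 50% |

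**3. Size of the food effect.** Ratios of Table 2 Day 1 (fed) to Table 1 (fasted):

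- 400 mg: Cmax 520/329 = 1.58; AUC24 3488/1933 = 1.80; fed AUC24 over fasted AUClast 3488/2135 = 1.63.
- 100 mg: Cmax 267/167 = 1.60; AUC24 1811/1160 = 1.56.
- 30 mg: Cmax 84/78 = 1.08; AUC24 664/543 = 1.22.

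The 400 mg fed row is marked as partial (4 subjects), with a Day 1 AUC24 CV of 58%. The 100 mg row is not marked partial, and its ratios also lie between 1.5 and 1.8. I use F = 1.5, 1.6 and 1.8 for the full-meal effect.

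**4. Minimum against minimum.** The documents do not say how exposure depends on the fraction eaten, f, so this step is an assumption. Linear scaling: E(f) = 1 + (F − 1)f, ratio E(0.5)/E(0.8). Log scaling: E(f) = F^f, ratio F^(−0.3). Extreme case: a 50% meal acts as fasted and an 80% meal as fully fed, ratio 1/F.

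| F | Linear | Log | Extreme |
|---|---|---|---|
| 1.5 | 1.25/1.40 = 0.893 | 0.885 | 0.667 |
| 1.6 | 1.30/1.48 = 0.878 | 0.868 | 0.625 |
| 1.8 | 1.40/1.64 = 0.854 | 0.838 | 0.556 |

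Under either scaling, exposure is about 11 to 16% lower at 50% than at 80%. The outer range is 0% (no difference in intake or effect) to about 44%.

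**5. Against the noise.** Table 2 gives a Day 10 AUC24 CV of 32% at 400 mg (partial data). Assuming the same CV in both populations, the log-scale SD is √ln(1 + 0.32²) = 0.312. With 14 psoriasis and 6 healthy active subjects, the standard error of the difference is 0.312 × √(1/14 + 1/6) = 0.152. A shift of ln 0.893 = −0.113 to ln 0.838 = −0.177 is 0.7 to 1.2 standard errors: enough to blur the comparison, not to dominate it.

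**The case against.** Only the permitted floor differs. Full meals are encouraged on every dosing day, subjects are housed through Day 28, and dosing is supervised, so actual Day 28 intake may be no lower than on MAD Day 10. That stands, and it is why the figures above are conditional. A careful site might also apply the higher minimum on Day 28 because it is plainly a profile day. That is possible, but it departs from the written list, and up to three sites could differ. Parts of the psoriasis schedule and its footnotes are not in the public text, so a Day 28 meal note there cannot be ruled out.

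A subtler argument is that a profile under the 50% floor better represents the exposure behind the Day 28 PASI response, since most psoriasis dosing days carry that floor. It is weak as a reading of this protocol. Section 4.6.1 ties the higher minimum to being a profile day, the high-fat subsection asks for about 80% on its Day 1, and Section 5.5 aims to standardise conditions on PK sampling days. If the sponsor does intend it, the text should say so.

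A reader might also infer more than the documents support:

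- That psoriasis exposure would be about 22 to 25% lower. That compares half a meal with a full one (at F = 1.8, 1.40/1.80 = 0.778 and 1.8^(−0.5) = 0.745). The protocol's own contrast is 50% with 80%.
- That the psoriasis safety margins are affected. Those in Section 1.3.4.1 rest on observed steady-state exposure in healthy subjects, and no passage recalculates them from psoriasis data.
- That the Cohort 2 dose decision turns on this. The planned interim analysis is of PASI, PK/PD modelling is only if needed, and the dose stays within the range established in healthy subjects. The PK review in Section 3.1.2 is a real link, but a limited one.

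**Conclusion.** The gap holds on the text available. The profile-day meal minimum is written for the MAD schedule, although the section also governs psoriasis, and the only psoriasis profile day falls under the lower minimum. The consequence is weaker control of a known food effect on the day that yields Cmax, AUCtau, Cav and CL/F for a secondary objective. It affects interpretation: the population comparison is descriptive, no test depends on it, and the primary safety endpoints do not rest on these parameters.

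The size is uncertain. About 11 to 16% lower exposure rests on three assumptions: a full-meal effect of 1.5 to 1.8, scaling with the fraction eaten, and subjects eating only the minimum. The range of 0 to about 44% shows how little the documents fix it. The 400 mg fed data behind the upper food-effect value come from 4 subjects. The point is worth correcting because the correction is so cheap.

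**What to change.** Reconcile the standard-meal paragraph of Section 4.6.1 with the psoriasis Schedule of Activities. Name the PK profile days by cohort, so that the protocol's own profile-day meal rule is tied to the day the psoriasis profile is taken (Day 28). Alternatively, state explicitly what minimum is intended on that day; the choice is the sponsor's. In either case, record the fraction of breakfast eaten on Day 28, so that a difference from MAD Day 10 can be read alongside actual intake.

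The cost is one line in the protocol and site meal instructions, plus one added data item per psoriasis subject. There is no new visit or sample, since subjects are already housed and dosed on site that day.
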